5.1.2 GSK2110183

GSK2110183 is a novel member of the N-alkyl pyrazole class of orally available kinase inhibitors and has been shown to be a potent, pan-AKT inhibitor, with potency (K_i^*) values for AKT 1, 2 and 3 kinases being 0.084, 2.0 and 2.6 nM, respectively. GSK2110183 exhibits a time-dependent inhibition of AKT with a dissociation half-life of 20 minutes. In vitro, GSK2110183 causes a concentration- and time-dependent reduction in phosphorylation of multiple proteins downstream of AKT such as GSK3, PRAS40, Forkhead (FOXO1/3a) and Caspase 9. Treatment of tumor cells with GSK2110183 resulted in a concentration-dependent increase in the nuclear translocation of the FOXO-3a transcription factor as a functional consequence of reduced phosphorylation of FOXO-3a. GSK2110183 has been shown to inhibit the proliferation of a range of tumor cell lines from multiple histologies including breast, hematological, colon, ovarian and prostate ($EC_{50} < 1 \mu M$). AKT signaling is inhibited in cell lines both sensitive and less sensitive to GSK2110183, suggesting that resistance to GSK2110183 is not due to a lack of AKT kinase inhibition. GSK2110183 has been shown to induce cycle arrest at G1 phase or apoptosis in a concentration-dependent manner depending on the cellular context.

GSK2110183 is an oral, low nanomolar pan-AKT kinase inhibitor given once daily in a phase 1, first-time-in-human (FTIH), two-stage study of patients with various hematologic malignancies. This study identified the maximal tolerated dose as 125mg daily with a cohort expansion Part 2 at this dose. The most common adverse events (AEs) were GI disorders (nausea 35%, dyspepsia 35%, diarrhea 19%, vomiting 12%) with very few drug-related Grade 3 AEs. The most frequent Grade 3 AEs were liver function test abnormalities (AST and ALT). Myelosuppression is uncommon at the 125mg dose (Grade 3-4 neutropenia 13%). Although AKT2 is an integral part of the insulin signaling pathway and hyperglycemia and hyperinsulinemia may be expected, no clinically significant hyperglycemia was observed in this study. Since GSK2110183 inhibits multiple cytochrome P450 (CYP) enzymes in vitro, there is potential for significant drug-drug interactions and therefore a variety of agents are prohibited or are to be used with caution during GSK2110183 use.

Four strengths of GSK2110183 (hydrochloride salt), formulated as a white to almost white solid, are provided as capsules equivalent to 1, 5, 25 or 100mg of GSK2110183 (free form).

5.2 Screening and Eligibility

The Investigator or designee is responsible for keeping a record of all subjects who sign an Informed Consent Form for entry into the study. All subjects will be screened for eligibility. Screening procedures are outlined in Section 2, Schedule of Study Assessments and must take place within 28 days prior to initiation of therapy.

Approximately 31 subjects with relapsed or refractory CLL will be screened for enrollment and must meet the eligibility criteria below.

Subjects must meet the following inclusion/exclusion criteria to be eligible for the study.

Inclusion criteria

Patients must fulfil all of the following criteria to be eligible for admission to the study:

- A confirmed diagnosis of B-cell CLL by IWCLL 2008 criteria (Appendix 1)
- Patients must have evidence of disease progression as evidenced by rapid doubling of peripheral lymphocyte count, progressive lymphadenopathy or hepatosplenomegaly, worsening anemia or thrombocytopenia, or progressive constitutional symptoms [including fatigue, weight loss, night sweats, fever (without infection)]
- Must be relapsed or refractory to at least one prior fludarabine-containing regimen (no maximum number of prior regimens).
- Age \geq 18 years.
- ECOG performance status of 0, 1 or 2 (Appendix 3)
- Signed the Informed Consent form
- Life expectancy of \geq 6 months
- Able to swallow and retain oral medication
- Normal HbA1C \leq 0.07
- Fasting blood sugar $<$ 7mmol/L

Exclusion criteria:

Subjects meeting any of the following criteria are excluded from this study:

- CLL therapy, including stem cell transplantation, within 4 weeks of study initiation. Corticosteroids alone may be administered up to seven days prior to the first dose of study drug.
- Treatment with any known non-marketed drug substance or experimental therapy within 5 terminal half-lives or 4 weeks prior to enrollment, whichever is longer, or currently participating in any other interventional clinical study
- Prior treatment with anti-CD20 monoclonal antibody or alemtuzumab within 3 months prior to start of therapy
- Known hypersensitivity to ofatumumab, GSK2110183, or any components therein.
- Anticoagulants are permitted only if the subject meets PTT and INR entry criteria while on anticoagulants (INR and PTT ≤ 1.5 times upper normal limit). Their use must be monitored in accordance with local institutional practice.
- Current use of any anti-platelet agent (e.g. dipyridamole, clopidogrel) other than aspirin (81mg daily).
- Current use of a prohibited medication based on potential drug-drug interaction – a complete list is found in Appendix 2
- Known CNS involvement with CLL
- Transformation to aggressive B-cell malignancy (e.g. large B-cell lymphoma, Richter's syndrome, prolymphocytic leukemia [PLL])
- "Active" autoimmune disease – prior history of autoimmune hemolysis (DAT positive or negative) or immune thrombocytopenia without current active autoimmune disease is allowed
- Subjects who have current active hepatic or biliary disease (with exception of patients with Gilbert's syndrome, asymptomatic gallstones, liver metastases or stable non-hepatitis B or C chronic liver disease per investigator assessment – please see below for Hepatitis B and C criteria)
- Previously diagnosed diabetes mellitus (Type 1 or 2)
- Other past or current malignancy. Subjects who have been free of malignancy for at least 5 years, or have a history of completely resected non-melanoma skin cancer, or successfully treated in situ carcinoma are eligible.

- Chronic or current infectious disease requiring systemic antibiotics, antifungal, or antiviral treatment such as, but not limited to, chronic renal infection, chronic chest infection with bronchiectasis, and tuberculosis.
- Any medical condition that would require long-term use (>1 month) of systemic corticosteroids during study treatment (excludes topical or inhaled corticosteroid use)
- History of significant cerebrovascular disease in the past 6 months or ongoing event with active symptoms or sequelae
- QTc \geq 470 msec on screening ECG
- Clinically significant cardiac disease including unstable angina, acute myocardial infarction within six months prior to study entry, congestive heart failure (NYHA III-IV), and arrhythmia unless controlled by therapy, with the exception of extra systoles or minor conduction abnormalities.
- Significant concurrent, uncontrolled medical condition including, but not limited to, renal, hepatic, gastrointestinal, endocrine, pulmonary, neurological, cerebral or psychiatric disease which in the opinion of the investigator may represent a risk for the patient.
- Any major surgery within the prior 4 weeks.
- Known HIV positive.
- Positive serology for Hepatitis B (HB) defined as a positive test for HBsAg. In addition, if negative for HBsAg but HBcAb positive (regardless of HBsAb status), a HB DNA test will be performed and if positive the subject will be excluded. Consult with a physician experienced in the care and management of study patients with hepatitis B to manage and treat patients who are HBcAb positive. Initiate antiviral therapy, if required.
- Positive serology for hepatitis C (HC) defined as a positive test for HCAb, in which case reflexively perform a HC RIBA immunoblot assay on the same sample to confirm the result.
- Screening laboratory values:
 - platelets \leq 30 x 10⁹/L
 - neutrophils \leq 0.7 x 10⁹/L

estimated GFR <40mL/min as calculated by the Cockcroft Gault formula

total bilirubin ≥ 1.5 times upper normal limit (unless due to a known history of Gilbert's disease)

ALT ≥ 2.5 times upper normal limit

alkaline phosphatase ≥ 2.5 times upper normal limit

INR and PTT ≥ 1.5 times upper normal limit

- Pregnant or lactating women. Women of childbearing potential must have a negative pregnancy test at screening.
- Women of childbearing potential, including women whose last menstrual period was less than one year prior to screening, unable or unwilling to use adequate contraception from study start to one year after the last dose of protocol therapy.

Adequate methods of contraception include use of an intrauterine device with an additional barrier method (**diaphragm with spermicidal gel or condoms with spermicide**), double-barrier methods—(diaphragm with spermicidal gel **and** condoms **with spermicide**), partner vasectomy, and total abstinence. Oral or depot hormonal contraceptives are not reliable due to potential drug-drug interactions. (The same contraceptive guidelines apply for male patients with a partner who is a woman of childbearing potential)

- Male subjects unable or unwilling to use adequate contraception methods from study start to one year after the last dose of protocol therapy.

5.3 Visit schedule and assessments

Screening Assessments and all on study scheduled visits and assessments are outlined in Section 2 Schedule of Study Assessments.

An unscheduled visit can occur at any time during the study. The date for the visit and any data generated must be recorded on the appropriate CRF. Source documents for these unscheduled visits must also be maintained.

At treatment discontinuation, subjects will undergo off study evaluations as per the Schedule of Assessments, Section 2. In addition, a safety assessment will be done approximately 28 days (+/- 4

days) post the last dose of protocol therapy. Thereafter, for patients who go off protocol treatment will be followed every three months to document time to relapse, next treatment, and death.

Pharmacokinetic sampling will take place on the following schedule (Appendix 6):

- Day 10 of the Lead-in Phase:
 - o Predose (before GSK2110183 dose), 0.5, 1, 2, 3, 4, 6, 8, 10-12, 14-22, and 24hr after (10-12hr and 14-22hr samples only where collection times are feasible)

- Cycle 2 Day 22 of the Treatment Phase (with 8th weekly dose of ofatumumab):
 - o Predose (before GSK2110183 dose), 0.5, 1, 2, 3, 4, 6, 8, 10-12, 14-22, and 24hr after (10-12hr and 14-22hr samples only where collection times are feasible)

5.3.1 Treatment assignments

All potential patients will be assessed by the study coordinator. Patients will be registered after completing an eligibility checklist. Protocol treatment is to begin within 7 working days of patient registration. Pre-study treatment evaluations will be performed as per Section 2, Schedule of Study Assessments.

5.4 Drug Administration

5.4.1 Dosing regimen - GSK2110183

GSK2110183 will be administered at a dose of 125mg orally daily as a single agent during the 10 day Lead-in Phase and then in combination with ofatumumab for 7 cycles/months (Treatment Phase), then as a single agent during the Maintenance Phase for an additional 11 cycles (max total duration 18 cycles/months). Subjects experiencing adverse events felt to be due to GSK2110183 may need study treatment modifications (See Section 5.5). Dose re-escalations for GSK2110183 are allowed at the discretion of the investigator and approval of the Study Medical Monitor.

5.4.2 Dosing regimen – Ofatumumab

Ofatumumab is a liquid concentrate for solution for infusion presented in glass vials. The ofatumumab infusions will be prepared in 1000mL sterile, pyrogen free 0.9% NaCl to yield a

0.3mg/mL and 2mg/mL ofatumumab concentration for the first and subsequent infusions, respectively.

The dosing of ofatumumab will initiate with an intravenous infusion of 300 mg on Day 1 followed by an infusion of 2000 mg weekly for 7 doses, followed 4 weeks later by an infusion of 2000 mg every 4 weeks for 4 additional doses. Each cycle will be of 4 weeks in duration.

Pre-medication before each ofatumumab infusion must be given within 30 minutes to 2 hours prior to the treatment:

Table 1 Pre-medication Requirements prior to Ofatumumab Infusions

Infusion #	Acetaminophen (PO) or equivalent	Antihistamine (IV or PO) diphenhydramine or equivalent	Glucocorticoid (IV) prednisolone or equivalent
1 st	1000 mg	50 mg	50 mg
2 nd	1000 mg	50 mg	50 mg
3 rd -N th	1000 mg	50 mg	0 – 50 mg*

*If the 2nd infusion has been completed without the subject experiencing any grade = 3 AEs, pre-medication with glucocorticoid may be reduced or omitted before the 3rd to Nth infusion at the discretion of the investigator.

During the ofatumumab infusion the patient should be monitored closely. Vital signs will be obtained preinfusion, at 30-minute intervals for the first hour during ofatumumab infusion, and then every hour until completion of infusion, including post-infusion. More frequent vital sign measurements should be performed if unstable, or if adverse events occur.

First Infusion of 300 mg Ofatumumab (CLL)

The first dose administered of ofatumumab in CLL should be 300 mg to minimize infusion reactions. The initial rate of the first infusion of 300 mg ofatumumab (0.3 mg/mL) should be 12 mL/h. If no infusion reactions occur the infusion rate should be increased every 30 minutes, to a maximum of 400 mL/h, according to Table 2. If this schedule is followed, the infusion duration will be approximately 4.6 hours.

Table 2 **Infusion rate at 1st ofatumumab infusion (300 mg)**

Time	mL/hour
0 – 30 minutes	12
31 – 60 minutes	25
61 – 90 minutes	50
91 – 120 minutes	100
121 - 150 minutes	200
151 - 180 minutes	300
181+ minutes	400

If an infusion reaction develops, the infusion should be temporarily slowed or interrupted. Upon restart, the infusion rate should be half of the infusion rate at the time the infusion was paused. If however, the infusion rate was 12 mL/hour before the pause, the infusion should be restarted at 12 mL/hour.

Thereafter, the infusion rate may be increased according to the judgment of the investigator, in the manner described in this section.

First Infusion of 2000 mg Ofatumumab

The initial rate of the first infusion of 2000 mg ofatumumab (2 mg/mL) should be 12 mL/h. If no infusion reactions occur the infusion rate should be increased every 30 minutes, to a maximum of 400 mL/h, according to Table 3. If this schedule is followed, the infusion duration will be approximately 5 hours.

Table 3 **Infusion rate at 1st ofatumumab infusion (2000 mg)**

Time	mL/hour
0 – 30 minutes	12
31 – 60 minutes	25
61 – 90 minutes	50
91 – 120 minutes	100
121 - 150 minutes	200
151 - 180 minutes	300
181+ minutes	400

If an infusion reaction develops, the infusion should be temporarily slowed or interrupted. Upon restart, the infusion rate should be half of the infusion rate at the time the infusion was paused. If, however, the infusion rate was 12 mL/hour before the pause, the infusion should be restarted at 12

mL/hour. Thereafter, the infusion rate may be increased according to the judgment of the investigator, in the manner described in this section.

Subsequent Infusions of 2000 mg Ofatumumab

If the previous infusion has been completed without grade ≥ 3 infusion-associated AEs, the subsequent infusion of the 2000 mg ofatumumab (2 mg/mL) can start at a rate of 25 mL/hour and should be doubled every 30 minutes up to a maximum of 400 mL/h, according to Table 4. Duration of the infusion will be approximately 4 hours if this schedule is followed. If the previous infusion has been completed with grade ≥ 3 infusion-associated AEs, the subsequent infusion should start at a rate of 12 mL/hour according to Table 2.

Table 4 Infusion rate at subsequent ofatumumab infusion

Time	mL/hour
0 – 30 minutes	25
31 – 60 minutes	50
61 – 90 minutes	100
91 – 120 minutes	200
121+ minutes	400

5.4.3. Management of Severe (Grade ≥ 3) Infusion Reactions to Ofatumumab

Infusion reactions tend to decrease with subsequent doses of ofatumumab. Most of the infusion / injection site reactions reported with ofatumumab have been mild or moderate; however, infusion reactions may be severe or even lead to death. If the investigator judges a grade ≥ 3 AE to be related to the infusion, the infusion must be interrupted and the appropriate clinical intervention begun. When the AE decreases to grade < 3 , the investigator may restart the infusion. Upon restarting the infusion, the infusion rate must be 12mL/hr for the first infusion or 25mL/hr for subsequent infusions, and may subsequently be increased according to the judgment of the investigator, as described in Table 3 and Table 4 (i.e. not more than doubled and no earlier than every 30 minutes). If the severity of the AE does not resolve to grade < 3 despite adequate clinical intervention, or the same AE increases to grade 3 on three occasions during one infusion, the subject should be withdrawn from treatment.

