8.2 Protocol deviations

When an emergency occurs that requires a deviation from the protocol for a subject, a deviation will be made only for that subject. A decision will be made as soon as possible to determine whether or not the subject (for whom the deviation from protocol was effected) is to continue in the study. The subject's medical records will completely describe the deviation from the protocol and state the reasons for such deviation. In addition, the Investigator will notify the IRB/EC/Health Canada in writing of such deviation from protocol.

Non-emergency minor deviations from the protocol will be permitted with approval of the Principal Investigator.

9 Data Management

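### After a grade 3 or higher reaction, section 5.4.3 can restart a later ofatumumab infusion at up to 2.08 times the rate just not tolerated

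*Combined protocol and SAP*

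**What the plan says.** Section 5.4.3 covers grade 3 or higher reactions. The infusion is interrupted, and once the event has fallen below grade 3 the investigator may restart it. If it is restarted, "the infusion rate must be 12mL/hr for the first infusion or 25mL/hr for subsequent infusions". The rate running when the reaction occurred plays no part. Later increases are left to the investigator's judgment, "as described in Table 3 and Table 4 (i.e. not more than doubled and no earlier than every 30 minutes".

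Section 5.4.2, on subsequent infusions of 2000 mg, normally starts at 25 mL/h (Table 4). If the previous infusion was completed with grade 3 or higher infusion-associated events, "the subsequent infusion should start at a rate of 12 mL/hour according to Table 2". Table 2 runs at 12 mL/h for the first 30 minutes.

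Section 5.4.2 also has a restart rule that does not depend on grade: resume at half the rate at the pause, with a floor. "If however, the infusion rate was 12 mL/hour before the pause, the infusion should be restarted at 12 mL/hour". The rule follows Table 2 and is repeated after Table 3, so it stands under the headings for the first 300 mg and first 2000 mg infusions. It is not repeated for later infusions.

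For the second infusion, "The initial rate of the first infusion of 2000 mg ofatumumab (2 mg/mL) should be 12 mL/h". Section 5.4.3 does not define its first infusion. The preparation sentence in 5.4.2 gives 0.3 and 2 mg/mL as the "ofatumumab concentration for the first and subsequent infusions", which there makes the 300 mg dose the first.

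Section 5.5.3.1 allows no ofatumumab dose reduction and refers infusional reactions to 5.4.3 for rate changes.

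**The concern.** A patient who reacted severely at one infusion is deliberately started at 12 mL/h at the next. If a second severe reaction comes early in that infusion, 5.4.3 as written requires any restart to be at 25 mL/h. The patients affected are those already known to react severely, and 5.4.3 itself acknowledges that infusion reactions can be fatal.

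Elsewhere in 5.4.2, moving from 12 to 25 mL/h takes 30 minutes without a reaction. Here the same step up would come straight after a grade 3 or higher reaction. A cautious restart at 12 mL/h would then be a departure from a rule worded as mandatory.

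**Working it through.** **Inputs.** Rate steps from Tables 2, 3 and 4 in section 5.4.2; infusion volume 1000 mL and concentration 2 mg/mL for the 2000 mg doses (5.4.2); restart rates from 5.4.3.

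**1. Check that the tables read correctly.** Duration = time in the 30-minute steps + remaining volume / 400 mL/h.
- Table 2: (12 + 25 + 50 + 100 + 200 + 300) × 0.5 = 343.5 mL in 3 h; then 656.5/400 = 1.64 h. Total 4.64 h, against a stated 4.6 h.
- Table 4: (25 + 50 + 100 + 200) × 0.5 = 187.5 mL in 2 h; then 812.5/400 = 2.03 h. Total 4.03 h, against a stated 4 h.

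Both stated durations are reproduced.

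**2. Which infusions.** There are 8 weekly and 4 monthly infusions, 12 in all. Numbers 3 to 12 are subsequent infusions on any reading, and 5.4.2 can start each of them at 12 mL/h.

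**3. Restart rate against running rate, for a subsequent infusion on Table 2 steps.** The last column is what the 5.4.2 restart rule would give if it applied.

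| Running rate (mL/h) | 5.4.3 restart | Ratio | 5.4.2 rule |
|---|---|---|---|
| 12 | 25 | 2.08 | 12 |
| 25 | 25 | 1.00 | 12.5 |
| 50 | 25 | 0.50 | 25 |
| 100 | 25 | 0.25 | 50 |
| 200 | 25 | 0.125 | 100 |
| 300 | 25 | 0.083 | 150 |
| 400 | 25 | 0.0625 | 200 |

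At 2 mg/mL, 12 mL/h is 24 mg/h and 25 mL/h is 50 mg/h. The ratio exceeds 1 only when the running rate is below 25 mL/h. On the schedule that is the first 30 minutes, when at most 12 × 0.5 = 6 mL (12 mg) has been given. It also happens off the schedule: an infusion already halved from 25 to 12.5 mL/h for a milder reaction would restart at 25/12.5 = 2.0 times its running rate.

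**4. Does other wording in 5.4.3 prevent this?** No. The limit to doubling applies to increases after the restart. The restart itself, at 2.08 times, slightly exceeds that limit.

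**5. Cost of restarting at 12 instead of 25 mL/h.** The extra 30-minute step delivers 6 mL, which saves 6/400 = 0.015 h at the end. Net: 0.5 − 0.015 = 0.485 h = 29.1 min. For 1000 mL from restart this is 4.64 against 4.16 h if later steps follow Table 2, and 4.52 against 4.03 h if they follow Table 4. Volume already given (at most 6 mL on schedule) shortens both arms of each comparison equally.

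**The case against.** The strongest objection is that no two written rules collide. The rule that 12 restarts at 12 belongs to the first 300 mg and first 2000 mg infusions. It reaches infusions 3 to 12 only if the instruction to use Table 2 also brings in the text after that table. This stands: a reader might infer a flat contradiction, but the documents support only an inconsistency of principle. The mandatory 25 mL/h does not depend on that inference, however, so the faster restart remains.

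Second, 5.4.3 can be read as a return to the opening rate of the relevant table: 12 for Table 3 and 25 for Table 4, the two tables it names. The first 2000 mg infusion would then restart at 12 mL/h. This is plausible, although the preparation sentence in 5.4.2 points the other way. A reader might infer that the second infusion is affected too; the text does not settle it. Even on this reading, 5.4.3 overlooks a later infusion moved back to Table 2.

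Third, there are safeguards. Restart is optional and requires the event to be below grade 3. Treatment ends if the event does not settle, or if the same event reaches grade 3 three times in one infusion. A footnote to the assessment schedule lets an infusion be split over two days. Section 8.2 adds: "Non-emergency minor deviations from the protocol will be permitted with approval of the Principal Investigator". These limit the risk. None changes the restart rate: the investigator's discretion covers whether to restart and how fast to increase afterwards.

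**Conclusion.** The point holds for infusions 3 to 12. After a grade 3 or higher reaction at the previous infusion and another while running below 25 mL/h, 5.4.3 requires any restart at 25 mL/h. That is 2.08 times the running rate at the 12 mL/h step and 2.0 times at 12.5 mL/h. The 12.5 mL/h case assumes that a milder reaction has already led to halving. At 25 mL/h the restart equals the running rate, and above that it is slower.

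Two further inferences should be resisted. The problem is not confined to the scheduled 12 mL/h step, because a slowed or halved infusion meets it too. And 10 of 12 infusions is a ceiling on where it can arise, not an estimate of how often: two severe reactions must occur in sequence, the documents give no frequency for that, and 5.4.3 says reactions tend to lessen with later doses.

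This is a minor safety correction that should be made. It has no bearing on response rate, sample size, error rates or any analysis.

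**What to change.** In section 5.4.3, directly after the 25 mL/h rate for subsequent infusions, add: *but never faster than the rate running when the reaction occurred (minimum 12 mL/h)*. In the same section, state that the first infusion covers both the 300 mg infusion and the first 2000 mg infusion.

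The cap leaves restarts unchanged for later infusions running at 25 mL/h or more. The definition settles the second infusion at 12 mL/h.

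The cost is a wording amendment and about 29 minutes more per affected infusion. The same applies to a restarted first 2000 mg infusion at which staff would now use 25 mL/h. No analysis, visit or data item changes.
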